9.1	PUBLISHED REFERENCES.....	75
9.2	UNPUBLISHED REFERENCES.....	76
10.	APPENDICES	77
11.	DESCRIPTION OF GLOBAL AMENDMENTS.....	78

ABBREVIATIONS

$\lambda_{z(N)}$	Terminal rate constant of the analyte in plasma (after the N th dose)
AE	Adverse event
AE SI	Adverse events of special interest
ANCOVA	Analysis of covariance
AUC _{0-24(N)}	Area under the concentration-time curve of the analyte in plasma over the time interval from 0 to 24h (after the N th dose)
BA	Bioavailability
BI	Boehringer Ingelheim
BLQ	Below limit of quantification
BMI	Body mass index (weight divided by height squared)
BP	Blood pressure
CA	Competent authority
CCL ₄	Carbon tetrachloride
CI	Confidence interval
C _{max(N)}	Maximum measured concentration of the analyte in plasma (after the N th dose)
CML	Clinical Monitor Local
CNS	Central nervous system
CRA	Clinical Research Associate
CRF	Case report form
CRO	Clinical Research Organisation
CTCAE	Common Terminology Criteria for Adverse Events
CTP	Clinical trial protocol
CTR	Clinical trial report
CTSU	Clinical Trial Supplies Unit
CV	Arithmetic coefficient of variation
DEDP	Drug exposure during pregnancy
DILI	Drug induced liver injury
DNA	Deoxyribonucleic acid
ECG	Electrocardiogram
EDTA	Ethylenediaminetetraacetic acid
ELISA	Enzyme-Linked Immunosorbent Assay
EOT	End of trial
FDA	Food and Drug Administration
FIH	First in human

Proprietary confidential information © 2017 Boehringer Ingelheim International GmbH or one or more of its affiliated companies

FOB	Functional observational battery
GCP	Good Clinical Practice
GFR	Glomerular filtration rate
GI	Gastro-intestinal
GLP	Good Laboratory Practice
gMEAN	Geometric mean
HCC	Hepatocellular carcinoma
HR	Heart rate
IB	Investigator's brochure
IEC	Independent Ethics Committee
IPV	Important protocol violations
IRB	Institutional Review Board
ISF	Investigator site file
LLOQ	Lower limit of quantification
MCD	Methionine-Choline deficient Diet
MedDRA	Medical Dictionary for Regulatory Activities
MRD	Multiple-rising dose
NBE	New biological entity
NC	Not calculated
NCE	New chemical entity
NOA	Not analysed
NOAEL	No observed adverse effect level
NOR	No valid result
NOS	No sample available
PD	Pharmacodynamic(s)
PE	Polyethylene
PK	Pharmacokinetic(s)
PKS	Pharmacokinetic parameter analysis set
p.o	per os
PP	Polypropylene
PR	Pulse rate
PTM	Planned time of the measurement
q.d.	Quaque die , once daily
QT	Time between start of the Q-wave and the end of the T-wave in an electrocardiogram
QTc	QT interval corrected for heart rate using the method of Fridericia (QTcF) or Bazett (QTcB)
QTcV	heart-rate corrected QT interval using Van de Water's formula
R	Reference treatment

Proprietary confidential information © 2017 Boehringer Ingelheim International GmbH or one or more of its affiliated companies

RDC	Remote Data Capture
REP	Residual effect period
SAE	Serious adverse event
SCR	Screening
SOC	System Organ Class
SOP	Standard Operating Procedure
SRD	Single-rising dose
SUSAR	Suspected Unexpected Serious Adverse Reaction
T	Test product or treatment
TDMAP	Trial Data Management and Analysis Plan
TEAE	Treatment-emergent adverse event
TMF	Trial master file
TS	Treated Set
TSAP	Trial statistical analysis plan
TSH	Thyroid stimulating hormone
ULN	Upper limit of normal

Proprietary confidential information © 2017 Boehringer Ingelheim International GmbH or one or more of its affiliated companies

2. RATIONALE, OBJECTIVES, AND BENEFIT - RISK ASSESSMENT

2.2 TRIAL OBJECTIVES

The primary objective of the current study is to investigate the safety and tolerability of BI 1467335 in healthy Japanese male subjects following oral administration of multiple rising doses of 3, 6 and 10 mg (for details see [Section 5.2](#)). The Caucasian group will receive 10 mg only.

A secondary objective is the exploration of the pharmacokinetics and pharmacodynamics of BI 1467335 in healthy Japanese and Caucasian male subjects.

A description of the endpoints to be determined, and the observations along with specific information as how to collect the data for that information, is provided in [Section 5](#).

3. DESCRIPTION OF DESIGN AND TRIAL POPULATION

3.1 OVERALL TRIAL DESIGN AND PLAN

This multiple rising dose trial will be randomised, double-blind, and placebo controlled within dose groups.

A total of 48 volunteers will participate in the trial according to three groups with 12 subjects in dose groups 1 & 2 and 24 subjects in dose group 3. Each of the sequential dose groups has one or two ethnic subgroups and within each of the subgroups 9 subjects will receive the active drug and 3 subjects will receive placebo. One dose is tested within each group.

The dose groups to be evaluated are as outlined in Table 3.1: 1 below.

Table 3.1: 1 Dose groups and subject numbers

Dose group	1	2	3	
Dose	3 mg q.d.	6 mg q.d.	10 mg q.d.	
Ethnicity	Japanese	Japanese	Japanese	Caucasian
No of subjects	12	12	12	12
Subjects receiving placebo	3	3	3	3
Subjects receiving active	9	9	9	9

The different dose groups will be investigated consecutively in ascending order of the doses in Japanese. The decision to proceed to the next dose group will be based upon the safety of the preceding dose group. Preliminary PK assessments as detailed in [Section 7.3.4](#) will be performed at 6 mg dose level before starting with 10 mg dose level.

The investigator is allowed to stop the further dose escalation in case the safety evaluation leads to concerns which would not allow higher dosing.

3.1.1 Administrative structure of the trial

The trial will be conducted at and in

The trial medication will be provided by the Clinical Trial Supplies Unit (CTSU), BI Pharma GmbH & Co. KG, Biberach, Germany.

On-site monitoring will be performed under the responsibility of Clinical Operations in Nippon BI.

Safety laboratory tests will be performed by the local laboratory of the trial site or/and at a CRO designated by the sponsor.

The analyses of BI 1467335 plasma concentrations will be performed at the Department of Drug Metabolism and Pharmacokinetics, BI Pharma GmbH & Co. KG, Biberach, Germany.

A central ECG laboratory will be selected to provide services for ECG evaluation as required for this protocol. The ECG device will be provided by the ECG service vendor. Please refer to [Section 5.2.4](#) for the details.

The trial is sponsored by Boehringer Ingelheim.

Boehringer Ingelheim has appointed a Trial Clinical Monitor, responsible for coordinating all required activities, in order to:

- manage the trial in accordance with applicable regulations and internal SOPs,
- direct the clinical trial team in the preparation, conduct, and reporting of the trial,
- order the materials as needed for the trial,
- ensure appropriate training and information of local clinical monitors (CML), Clinical Research Associates (CRAs), and Investigators of participating countries.

Data Management and Statistical Evaluation will be done by BI according to BI SOPs.

Tasks and functions assigned in order to organise, manage, and evaluate the trial will be defined according to BI SOPs. A list of responsible persons and relevant local information (as protocol reference, if applicable) can be found in the ISF (Investigator site file).

Relevant documentation on the participating (Principal) Investigators and other important participants, including their curricula vitae, will be filed in ISF.

3.2 DISCUSSION OF TRIAL DESIGN, INCLUDING THE CHOICE OF CONTROL GROUP

For multiple rising dose trials, the design described in [Section 3.1](#) is viewed favourable under the provision not to expose the subjects involved to undue risks since the main study objective is to investigate safety and tolerability as well as pharmacokinetics of BI 1467335.

With the rising dose design, double-blind conditions regarding the subjects' treatment (active or placebo) are maintained within each dose group, however the current dose level will be known to subjects and investigators.

Proprietary confidential information © 2017 Boehringer Ingelheim International GmbH or one or more of its affiliated companies

The disadvantage of this trial design is a possible observer bias with regard to the dose depending effects as well as time effects but it has the virtue of minimising subject risk by sequentially studying ascending doses. This implicates a confounding factor concerning statistical comparisons between the dose levels.

The resulting group sizes (nine subjects per active treatment group for doses 3mg and 6 mg, nine subjects per active treatment group per ethnicity for 10 mg) are in general considered as sufficient for the exploratory evaluation of pharmacokinetics.

It is standard in trials involving healthy volunteers to include a placebo group as control for the evaluation of safety, tolerability and pharmacokinetic effects. Each dose group consists of 12 subjects per ethnicity with 9 on active treatment, and 3 on placebo. The placebo control group includes all subjects of all dose groups treated with placebo.

3.3 SELECTION OF TRIAL POPULATION

It is planned that 48 healthy male subjects will enter the study. Based on the known safety profile and general applicability to a variety of potential indications that BI 1467335 is pursuing, healthy volunteer are chosen in this phase I study. Healthy subjects as a Phase I trial population are ideal because they provide relatively stable physiological, biochemical, and hormonal conditions. In these subjects there is absence of disease-related variations and concomitant medications. Healthy subjects can be tested under standardised conditions and in an environment that allows repeated testing.

3.3.1 Main diagnosis for study entry

The study will be performed in healthy male subjects.

3.3.2 Inclusion criteria

Subjects will only be included into the trial, if they meet the following criteria:

1. Healthy male subjects according to the investigator's assessment, based on a complete medical history including a physical examination, vital signs (BP, PR), 12-lead ECG, and clinical laboratory tests
2. Japanese ethnicity or Caucasian, according to the following criteria:
 - Japanese; born in Japan, have lived outside of Japan <10 years, and have parents and grandparents who were all born in Japan
 - Caucasian
3. Age of 20 to 45 years (incl.)
4. BMI of 18.5 to 25 kg/m² (incl.) for Japanese and 18.5 to 29.9 kg/m² (incl.) for Caucasian
5. Signed and dated written informed consent by date of Visit 1 in accordance with GCP and local legislation.
6. Male subjects who agree to minimize the risk of female partners becoming pregnant by fulfilling any of the following criteria starting from at least 30 days before the first administration of trial medication and until 30 days after trial completion:

Proprietary confidential information © 2017 Boehringer Ingelheim International GmbH or one or more of its affiliated companies

- Use of adequate contraception, e.g. any of the following methods *plus* condom:
combined oral contraceptives, intrauterine device
- Vasectomised (vasectomy at least 1 year prior to enrolment)
- Surgically sterilised (including hysterectomy) female partner

3.3.3 Exclusion criteria

Subjects will not be allowed to participate if any of the following general criteria apply:

1. Any finding in the medical examination (including BP, PR or ECG) is deviating from normal and judged as clinically relevant by the investigator
2. Any laboratory value outside the reference range that the investigator considers to be of clinical relevance
3. Any evidence of a concomitant disease judged as clinically relevant by the investigator
4. Gastrointestinal, hepatic, renal, respiratory, cardiovascular, metabolic, immunological or hormonal disorders
5. Surgery of the gastrointestinal tract that could interfere with kinetics of the trial medication (except appendectomy and simple hernia repair)
6. Diseases of the central nervous system (including but not limited to any kind of seizures or stroke), and other relevant neurological or psychiatric disorders
7. History of relevant orthostatic hypotension, fainting spells, or blackouts
8. Chronic or relevant acute infections including HIV, viral hepatitis and (or) tuberculosis or evidence of tuberculosis infection as defined by a positive QuantiFERON TB-Gold (or T-SPOT) test. Subjects with a positive QuantiFERON TB-Gold (or T-SPOT) test will not participate in the study.
9. History of relevant allergy or hypersensitivity (including allergy to the trial medication or its excipients)
10. Intake of biologic agents other than current study medication or drugs considered likely to interfere with the safe conduct of the study
11. Intake of drugs with a long half-life (more than 24 h) within 30 days or less than 10 half-lives of the respective drug prior to administration of trial medication
12. Within 10 days prior to administration of trial medication, use of drugs that might reasonably influence the results of the trial or that might prolong the QT/QTc interval
13. Participation in another trial (including bioequivalence trial) with an investigational drug within 90 days or 5 half-lives (whichever is greater) prior to planned administration of trial medication
14. Smoker (more than 10 cigarettes or 3 cigars or 3 pipes per day)
15. Inability to refrain from smoking on specified trial days
16. Alcohol abuse (consumption of more than 30 g per day)
17. Drug abuse or positive drug screening
18. Blood donation of more than 200 mL within 30 days prior to administration of trial medication or intended donation during the trial

Proprietary confidential information © 2017 Boehringer Ingelheim International GmbH or one or more of its affiliated companies

19. Intention to perform excessive physical activities within one week prior to administration of trial medication or during the trial
20. Inability to comply with dietary regimen of trial site
21. A marked baseline prolongation of QT/QTc interval (such as QTc intervals that are repeatedly greater than 450 ms) or any other relevant ECG finding at screening
22. A history of additional risk factors for Torsades de Pointes (such as heart failure, hypokalemia, or family history of Long QT Syndrome)
23. Have received any live bacterial or live viral vaccination in the 12 weeks prior to the date of screening. Subjects must agree not to receive a live bacterial or live viral vaccination during the study and up to 12 months after the last administration of study drug
24. Have received Bacille Calmette-Guerin (BCG) vaccination in the 12 months prior to the date of screening. Subjects must agree not to receive BCG vaccination during the study and up to 12 months after the last administration of study drug
25. Subject is assessed as unsuitable for inclusion by the investigator, for instance, because considered not able to understand and comply with study requirements, or has a condition that would not allow safe participation in the study
26. Signs of cataract at screening by slit lamp test

For study restrictions, refer to [Section 4.2.2](#).

3.3.4 Removal of subjects from therapy or assessments

3.3.4.1 Removal of individual subjects

An individual subject is to be removed from the trial if:

1. The subject withdraws consent, without the need to justify the decision
2. The subject needs to take concomitant drugs that interfere with the investigational product or other trial medication
3. The subject is no longer able to participate for other medical reasons (such as surgery, adverse events, or diseases)
4. An AE or clinically significant laboratory change or abnormality occurred that the investigator judges to warrant discontinuation of treatment. This may include cases of sustained symptomatic hypotension (BP <90/50 mmHg) or hypertension (BP >180/100 mmHg) or of clinically relevant changes in ECG requiring intervention as well as unexplained liver enzyme elevations at any time during the trial.

In addition to these criteria, the physician may discontinue subjects at any time based on his or her clinical judgment.

A subject can also be removed from the trial if eligibility criteria are being violated or if the subject fails to comply with the protocol (for instance, by non-adherence to dietary rules, or non-attendance at study assessments).

Proprietary confidential information © 2017 Boehringer Ingelheim International GmbH or one or more of its affiliated companies

If a subject is removed from or withdraws from the trial prior to first administration of trial medication, the data of this subject will not be entered in the case report form (CRF) or trial database and will not be reported in the clinical trial report (CTR). The only exception to this rule is when the subject had an AESI and/or SAE that the investigator considers related to the screening procedure. If a subject is removed from or withdraws from the trial after first administration of trial medication, this will be documented and the reason for discontinuation must be recorded in the CRF. In this case, the data will be included in the CRF/trial database and will be reported in the CTR. At the time of discontinuation a complete EOT examination will be performed if possible and the information will be recorded in the CRFs. These discontinuations will be discussed in the CTR.

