5.2 SAFETY

5.2.1 Endpoints of safety

Primary endpoint to assess safety and tolerability of BI 1467335 is the number [N (%)] of subjects with drug-related AEs.

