5.2.2.2 Adverse event collection and reporting

AE Collection

Upon enrolment into a trial, the subject's baseline condition is assessed (for instance, by documentation of medical history/concomitant diagnoses), and relevant changes from baseline are noted subsequently.

[figure not shown]
Subjects will be required to report spontaneously any AEs as well as the time of onset, end, and intensity of these events. In addition, each subject will be regularly assessed by the medical staff throughout the clinical trial and whenever the investigator deems necessary. As a minimum, subjects will be questioned for AEs (and concomitant therapies) at the time points indicated in the [Flow Chart](#). Assessment will be made using non-specific questions such as 'How do you feel?'. Specific questions will be asked wherever necessary in order to more precisely describe an AE.

A careful written record of all AEs shall be kept by the investigator in charge of the trial. Records of AEs shall include data on the time of onset, end time, and intensity of the event as well as any treatment or action required for the event and its outcome.

The following must be collected and documented on the appropriate eCRF by the investigator:

Proprietary confidential information © 2017 Boehringer Ingelheim International GmbH or one or more of its affiliated companies

- From signing the informed consent onwards through the Residual Effect Period (REP), until individual subject's EOT:
 - all AEs (serious and non-serious) and all AESIs.
 - The only exception to this rule are AEs (serious and non-serious) and AESIs in Phase I trials in healthy volunteers, when subjects discontinue from the trial due to screening failures prior to administration of any trial medication. In these cases, the subjects' data must be collected at trial site but will not be entered in the CRF or trial database and will not be reported in the CTR.
- After the individual subject's EOT:
the investigator does not need to actively monitor the subject for AEs but should only report relevant SAEs and relevant AESIs of which the investigator may become aware of.

The REP for BI 1467335, when measurable drug levels or PD effects are still likely to be present after the last administration, is not known at this early stage of development. Therefore, all AEs reported until the trial termination date (last per protocol contact) will be considered on treatment; please see [Section 7.3.3](#).

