6. INVESTIGATIONAL PLAN

6.1 VISIT SCHEDULE

All visits must be performed as specified in Flow Chart. The investigator/sponsor can decide to perform an unscheduled visit if deemed necessary for any valid reasons.

Further details of measurement performed during the study are specified under [Section 5](#).

Time windows are permitted as follows:

- General medical examination: at screening (1 to 21 days prior to Day1) and at the end-of-trial evaluation (within 14 to 20 days after last drug administration).
- BP and PR: ± 15 min (0:30, 0:45, 1:00, 2:00) and ± 30 min (4:00, 8:00, 12:00) on Day 1, Day 14 and Day 28, ± 60 min on other days and up to 3 hours prior to drug administration if indicated "before drug administration"
- ECG: ± 15 min (0:15, 0:30, 0:45, 1:00, 1:30, 2:00) and ± 30 min (4:00, 8:00, 12:00) on Day 1, Day 14 and Day 28, ± 60 min on other days.
ECGs on Day 1, 2, 14, 15, 28 and 29: for the second and third ECG a time interval of 1-3 min between ECGs should be maintained
- Laboratory/urinalysis: Up to 3 hours prior to drug administration if indicated "before drug administration". Urinalysis test can be done up to 3 hours prior to drug administration at some other time points indicated in the flow chart.
- Pharmacokinetic blood sampling for predose concentration in multiple dose part: ± 5 min (has to be done before drug administration)

Other pharmacokinetic blood sampling / urine collection: For planned individual plasma concentration sampling times refer to Flow Chart. While these nominal times should be adhered to as closely as possible, the actual sampling times will be recorded and used for the calculation of pharmacokinetic parameters.

The designation "before" on Day 1 refers to the time period of 3 hours before drug administration (see [Flow Chart](#)), i.e., study measurements and assessments scheduled to occur "before" have to be performed and completed within 3 hours prior to drug administration.

Relevant time violations will be identified and their handling discussed no later than at the (B)RPM.

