6.2.3 End of trial and follow-up period

For AE assessment, laboratory tests, recording of ECG, vital signs and body weight, and physical examination during the EOT period, see [Sections 5.2.2 to 5.2.5](#).

Subjects who discontinue treatment before the end of the planned treatment period should undergo the EOT visit.

All abnormal values (including laboratory parameters) that are judged clinically relevant by the investigator will be monitored using the appropriate tests until a return to a medically acceptable level is achieved. All (S)AEs, including those persisting after individual subject's end of trial must be followed up until they have resolved, have been sufficiently characterized, or no further information can be obtained.

In the case of a subject's discontinuation from the trial, the subject will be followed-up until the investigator or sub-investigator is convinced of the subject's safety. When follow-up is not possible or comes to an end, it should be formally completed after discussion with the sponsor. If a subject stops attending trial assessments, the investigator should assess the subject's status as comprehensively as possible and the well-being of the subject should be monitored. However, if the subject withdraws from the trial, it is the subject's choice whether or not to participate; he or she cannot be compelled.

The end of the trial as a whole is defined by the 'last regular visit completed by last subject' or 'end date of the last open AE' or 'date of the last follow-up test' or 'date of an AE has been decided as sufficiently followed-up', whichever is latest.

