## **6. GENERAL ANALYSIS DEFINITIONS**

### **6.1 TREATMENTS**

For basic study information on treatments to be administered, assignments of dose groups, and selection of doses, cf. Section 4 of the CTP.

Subjects were treated with 3 mg, 6 mg or 10 mg of BI 1467335 (test treatment, T) or placebo (reference treatment, R) once daily over 28 days. Three placebo groups will be defined: Placebo for Japanese, Placebo for Caucasians and Total placebo. Placebo for Japanese will be defined as a pooled group of the Japanese subjects receiving placebo treatment in the three dose groups. Placebo for Caucasians will be defined as the placebo subjects in the 10 mg dose group for Caucasians (which comprises all placebo-treated Caucasian subjects). Total placebo will be defined as one pooled placebo group (i.e. no distinction between dose groups and ethnicity will be made for placebo subjects).

For statistical analysis of AEs, safety laboratory data, vital signs and ECG, the following analysis phases are defined for each subject:

Table 6.1: 1 Flow chart of analysis phases for statistical analyses of AEs, safety laboratory data, vital signs and ECG

| Study analysis phase | Label  | Start (inclusive)                               | End (exclusive)                                    |
|----------------------|--|---|--|
| Screening            | Screening  | Date of informed consent                        | Date/time of first administration of study drug    |
| On-treatment         | Placebo,
3 mg BI for
Japanese,
6 mg BI for
Japanese,
10 mg BI for
Japanese
or 10 mg BI for
Caucasians,
respectively | Date/time of first administration of study drug | 0:00 on day after subject's trial termination date |

CTR Section 15, Appendix 16.1.9.2.8.2 and Appendix 16.1.9.2.8.3 AE displays will present results for the on-treatment phase only.

In CTR Section 15 AE tables (but not in Appendix 16.1.9.2.8.2 and Appendix 16.1.9.2.8.3 AE tables), the following totals will be provided in addition:

- "**Total BI**", defined as the total over all on-treatment phases involving BI, i.e., "3 mg BI for Japanese" + "6 mg BI for Japanese" + "10 mg BI for Japanese" + "10 mg BI for Caucasians"
- "**Total BI for Japanese**", defined as the total over all on-treatment phases involving BI, i.e., "3 mg BI for Japanese" + "6 mg BI for Japanese" + "10 mg BI for Japanese"

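### The protocol gives conflicting times for the EOT of subjects who stop early, so their post-dose AE collection may be about 0 days against 14 to 20 in completers

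*Protocol*

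**What the plan says.** Three places in the protocol bear on when an early stopper has his EOT.

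- Section 3.3.4.1, for a subject removed or withdrawing after first dosing: "At the time of discontinuation a complete EOT examination will be performed if possible".
- Section 6.1, among the permitted time windows, places the general medical examination "at the end-of-trial evaluation (within 14 to 20 days after last drug administration"). The text is not limited to subjects who complete 28 days. The Flow Chart shows the EOT on Days 42 to 48.
- Section 6.2.3: "Subjects who discontinue treatment before the end of the planned treatment period should undergo the EOT visit". No time is given.

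The EOT date matters because Section 5.2.2.2 collects all AEs "From signing the informed consent onwards through the Residual Effect Period (REP), until individual subject's EOT". After that point "the investigator does not need to actively monitor the subject for AEs but should only report relevant SAEs and relevant AESIs". The same section says the residual effect period is not known and that "all AEs reported until the trial termination date (last per protocol contact) will be considered on treatment". SAP Section 6.1 closes the on-treatment phase at "0:00 on day after subject's trial termination date". Neither document sets a fixed post-dose interval for AE analysis.

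On the endpoint, Section 5.2.1 reads: "Primary endpoint to assess safety and tolerability of BI 1467335 is the number [N (%)] of subjects with drug-related AEs". Section 7.3.1 analyses it descriptively on the Treated Set, so early stoppers stay in the denominator.

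**The concern.** If the EOT is done on the day a subject is taken off the trial, his active AE collection stops close to his last dose, while a completer is observed for at least two more weeks. Both then enter the same crude percentage. A new non-serious drug-related AE that begins a few days after dosing stops would be recorded in one subject and could go unrecorded in the other.

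The loss runs in one direction, towards fewer AEs. It affects the primary count, the AE tables and the tables by maximum CTCAE grade. The groups are small, and Section 3.1 bases the step to the next dose group on the safety of the preceding one, so a single unrecorded subject is visible in the result. Two sites, or one site on two occasions, could also apply different EOT times and each be within the protocol.

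**Working it through.** **1. The plan's own window.** The Flow Chart puts the last dose at 648:00 h. 648 / 24 = 27, and Day 1 starts at 0 h, so this is Day 28. The EOT is on Days 42 to 48: 42 − 28 = 14 and 48 − 28 = 20. This reproduces the 14 to 20 days of Section 6.1.

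**2. Post-dose AE collection under each text.** The 3.3.4.1 row assumes that the examination falls close to the last dose.

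| Subject and text applied | Post-dose days of active collection |
|---|---|
| Completer (6.1, Flow Chart) | 14 to 20 |
| Early stopper, 3.3.4.1 | about 0 |
| Early stopper, 6.1 counted from his own last dose | 14 to 20 |
| Early stopper, 6.2.3 alone | not stated |

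**3. Total window, and how much of the gap is post-dose.** Take a stop on Day 10. Under 3.3.4.1 the window from Day 1 is 10 days, against 42 to 48 for a completer. The gap is 42 − 10 = 32 to 48 − 10 = 38 days. Of this, 28 − 10 = 18 days are dosing days that never took place; the remaining 14 to 20 are post-dose follow-up. Only the second part is a question of AE collection. With the 6.1 window counted from his last dose, this subject would have 10 + 14 = 24 to 10 + 20 = 30 days.

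**4. Who can be missed in the primary count.** The endpoint counts subjects.

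- A subject who stops because of a drug-related AE is already counted. Later events can change only the AE and grade tables.
- A subject who stops for another reason (interfering co-medication, an unrelated medical reason, non-compliance, an eligibility violation) can be missed if his first drug-related AE is non-serious and starts after his EOT.
- A subject who withdraws consent cannot be required to continue, so no wording recovers his window.

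**5. Size of one missed subject.** 1/9 = 11.1 points in an active group; 1/12 = 8.3 points in the pooled placebo group. These are the effects of a certain miss.

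**6. Expected size, under assumptions that are not in the documents.** Assume a constant hazard h that continues after dosing stops, completer risk p over 45 days (midpoint of 42 to 48), 17 post-dose days lost (midpoint of 14 to 20), and nothing captured by other follow-up. Then h = −ln(1 − p)/45, and for a stop on Day 7 the chance of missing a first event is exp(−7h) × [1 − exp(−17h)].

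| p | Chance of a miss per stopper | Points in a group of 9 |
|---|---|---|
| 10% | 3.8% | 0.4 |
| 30% | 11.9% | 1.3 |
| 50% | 20.7% | 2.3 |

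The last column is the chance divided by 9. It applies per stopper of the exposed kind.

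**The case against.** The strongest reply is that the protocol can be read consistently. Section 6.1 counts from the last drug administration without restriction, and 6.2.3 requires the EOT visit after an early treatment stop. Together they would give a stopper an EOT 14 to 20 days after his own last dose, with the 3.3.4.1 examination as an additional one. This reading is available, and no text says that 3.3.4.1 overrides the others. But no text says the reverse either. Section 3.3.4.1 is the specific provision, it calls the examination a complete EOT, and its fourth criterion removes from the trial a subject whose AE warrants stopping treatment. It therefore cannot be set aside as covering only subjects who leave by choice.

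A second reply is that AE information does not simply end. Relevant SAEs and AESIs are still reported after EOT, ongoing AEs are followed, and 6.2.3 follows a discontinued subject until the investigator is satisfied of his safety, which could move the last per-protocol contact. All of this stands, so a reader should not infer that AE reporting stops altogether. The follow-up, however, is discretionary, has no minimum length, and does not say that new non-serious AEs are collected.

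Third, the trial is descriptive, no hypothesis is tested, discontinuations are discussed in the report, and Section 3.3.5 allows replacement of some subjects, which would raise the denominator above 9 and lower the effect of one miss. This limits the consequence; it does not settle which EOT applies.

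**Conclusion.** The point holds as a conflict on EOT timing with a consequence for AE ascertainment. If 3.3.4.1 is followed, early stoppers have about 0 post-dose days of active collection against 14 to 20 in completers. The primary percentage can be understated by at most 11.1 points per missed subject in an active group of 9, and only for a subject who stops for a reason other than a drug-related AE and then has a first such event that goes unrecorded. The expected effect is smaller: 0.4 to 2.3 points per exposed stopper under the assumptions above. The AE and maximum-grade tables are exposed for any early stopper. The documents give no dropout rate, so the number of subjects concerned is unknown.

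Three stronger readings are tempting and not supported.

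- That the primary count misses the subjects with the worst tolerability: those who stop for a drug-related AE are already in it.
- That the protocol chose 14 to 20 days because the residual effect period is unknown, or calls that length necessary: Section 5.2.2.2 uses the unknown period only to justify assigning every AE up to termination to treatment.
- That the whole difference in observation time is a collection fault: part of it is dosing that did not happen.

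The change is worth making because it is cheap and the ambiguity acts in one direction.

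**What to change.** Reconcile Protocol 3.3.4.1, 5.2.2.2, 6.1 and 6.2.3 so that they give one rule for AE collection. For a subject who stops trial drug without withdrawing consent:

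- record the examination at discontinuation as a separate assessment, not as the EOT;
- run AE collection to the protocol's existing EOT window, counted from that subject's last dose;
- tie the trial termination date to that EOT contact, so that the SAP on-treatment phase follows without a change to its definition.

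This equalises post-dose AE follow-up. It does not equalise total time at risk, and the report should say so where early stoppers occur.

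The slit-lamp window in the Flow Chart notes and Section 5.2.5.3, which runs from Day 29 to EOT, is empty for a subject whose EOT falls before Day 29. Those passages must also be reconciled.

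Cost: protocol wording, and one already-defined EOT contact for the few subjects who stop early. Nothing changes for completers.
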